9. STUDY MANAGEMENT

9.1 Compliance

9.1.1 Compliance with the Protocol and Protocol Revisions

The study shall be conducted as described in this approved protocol. All revisions to the protocol must be discussed with, and be prepared by, BMS. The investigator should not implement any deviation or change to the protocol without prior review and documented approval/favorable opinion from the IRB/IEC of an amendment, except where necessary to eliminate an immediate hazard(s) to study participants.

If a deviation or change to a protocol is implemented to eliminate an immediate hazard(s) prior to obtaining IRB/IEC approval/favorable opinion, as soon as possible the deviation or change will be submitted to:

- IRB/IEC for review and approval/favorable opinion
- BMS
- Regulatory Authority(ies), if required by local regulations

Documentation of approval signed by the chairperson or designee of the IRB(s)/IEC(s) must be sent to BMS.

If an amendment substantially alters the study design or increases the potential risk to the subject: (1) the consent form must be revised and submitted to the IRB(s)/IEC(s) for review and approval/favorable opinion; (2) the revised form must be used to obtain consent from participants currently enrolled in the study if they are affected by the amendment; and (3) the new form must be used to obtain consent from new participants prior to enrollment. If the revision is done via an administrative letter, investigators must inform their IRB(s)/IEC(s).

9.1.2 Monitoring

BMS representatives will review data centrally to identify potential issues to determine a schedule of on-site visits for targeted review of study records.

Representatives of BMS must be allowed to visit all study site locations periodically to assess the data quality and study integrity. On site they will review study records and directly compare them with source documents, discuss the conduct of the study with the investigator, and verify that the facilities remain acceptable. Certain CRF pages and/or electronic files may serve as the source documents.

In addition, the study may be evaluated by BMS internal auditors and government inspectors who must be allowed access to CRFs, source documents, other study files, and study facilities. BMS audit reports will be kept confidential.

The investigator must notify BMS promptly of any inspections scheduled by regulatory authorities, and promptly forward copies of inspection reports to BMS.

9.1.2.1 Source Documentation

The Investigator is responsible for ensuring that the source data are accurate, legible, contemporaneous, original and attributable, whether the data are hand-written on paper or entered electronically. If source data are created (first entered), modified, maintained, archived, retrieved, or transmitted electronically via computerized systems (and/or any other kind of electronic devices) as part of regulated clinical trial activities, such systems must be compliant with all applicable laws and regulations governing use of electronic records and/or electronic signatures. Such systems may include, but are not limited to, electronic medical/health records (EMRs/EHRs), AE tracking/reporting, protocol required assessments, and/or drug accountability records).

When paper records from such systems are used in place of electronic format to perform regulated activities, such paper records should be certified copies. A certified copy consists of a copy of original information that has been verified, as indicated by a dated signature, as an exact copy having all of the same attributes and information as the original.

9.1.3 Investigational Site Training

Bristol-Myers Squibb will provide quality investigational staff training prior to study initiation. Training topics will include but are not limited to: GCP, AE reporting, study details and procedure, electronic CRFs, study documentation, informed consent, and enrollment of WOCBP.

9.2 Records

9.2.1 Records Retention

The investigator must retain all study records and source documents for the maximum period required by applicable regulations and guidelines, or institution procedures, or for

the period specified by BMS, whichever is longer. The investigator must contact BMS prior to destroying any records associated with the study.

BMS will notify the investigator when the study records are no longer needed.

If the investigator withdraws from the study (eg, relocation, retirement), the records shall be transferred to a mutually agreed upon designee (eg, another investigator, IRB). Notice of such transfer will be given in writing to BMS.

9.2.2 Study Drug Records

It is the responsibility of the investigator to ensure that a current disposition record of study drug (inventoried and dispensed) is maintained at the study site to include investigational product and the following non-investigational product(s): ipilimumab. Records or logs must comply with applicable regulations and guidelines and should include:

- amount received and placed in storage area
- amount currently in storage area
- label identification number or batch number
- amount dispensed to and returned by each subject, including unique subject identifiers
- amount transferred to another area/site for dispensing or storage
- non-study disposition (e.g., lost, wasted)
- amount destroyed at study site, if applicable
- amount returned to BMS
- retain samples for bioavailability/bioequivalence, if applicable
- dates and initials of person responsible for Investigational Product dispensing/accountability, as per the Delegation of Authority Form.

BMS will provide forms to facilitate inventory control if the investigational site does not have an established system that meets these requirements.

9.2.3 Case Report Forms

An investigator is required to prepare and maintain adequate and accurate case histories designed to record all observations and other data pertinent to the investigation on each individual treated or entered as a control in the investigation. Data that are derived from source documents and reported on the CRF must be consistent with the source documents or the discrepancies must be explained. Additional clinical information may be collected and analyzed in an effort to enhance understanding of product safety. CRFs may be requested for AEs and/or laboratory abnormalities that are reported or identified during the course of the study.

For sites using the BMS electronic data capture tool, electronic CRFs will be prepared for all data collection fields except for fields specific to SAEs and pregnancy, which will be reported on the paper or electronic SAE form and Pregnancy Surveillance form, respectively. Spaces may be left blank only in those circumstances permitted by study-specific CRF completion guidelines provided by BMS.

The confidentiality of records that could identify participants must be protected, respecting the privacy and confidentiality rules in accordance with the applicable regulatory requirement(s).

The investigator will maintain a signature sheet to document signatures and initials of all persons authorized to make entries and/or corrections on CRFs.

The completed CRF, including any paper or electronic SAE/pregnancy CRFs, must be promptly reviewed, signed, and dated by the investigator or qualified physician who is a sub-investigator and who is delegated this task on the Delegation of Authority Form. For electronic CRFs, review and approval/signature is completed electronically through the BMS electronic data capture tool. The investigator must retain a copy of the CRFs including records of the changes and corrections.

Each individual electronically signing electronic CRFs must meet BMS training requirements and must only access the BMS electronic data capture tool using the unique user account provided by BMS. User accounts are not to be shared or reassigned to other individuals.

APPENDIX 1 RECIST 1.1 AND IMMUNE RESPONSE CRITERIA

RECIST version 1.1* and irRC/irRECIST** will be used in this study for assessment of tumor response. While either CT or MRI may be utilized, as per RECIST 1.1, CT is the preferred imaging technique in this study.

* As published in the European Journal of Cancer:

E.A. Eisenhauer, P. Therasse, J. Bogaerts, L.H. Schwartz, D. Sargent, R. Ford, J. Dancey, S. Arbuck, S. Gwyther, M. Mooney, L. Rubinstein, L. Shankar, L. Dodd, R. Kaplan, D. Lacombe, J. Verweij. New response evaluation criteria in solid tumors: Revised RECIST guideline (version 1.1). *Eur J Cancer*. 2009 Jan;45(2):228-47.

** As published in Clinical Cancer Research:

In addition, volumetric analysis will be explored by central review for response assessment.

APPENDIX 2 DOSE REDUCTION FOR ENCORAFAENIB RELATED ADVERSE EVENTS

Action	Recommended Dose
First Dose Reduction	300mg (four 75mg capsules) PO once daily
Second Dose Reduction	225mg (three 75mg capsules) PO once daily
Third Dose Reduction	150mg (two 75mg capsules) PO once daily
Subsequent Modification	Discontinue

Severity of Adverse Event	Dose Modification
New Primary Malignancies	
Non-cutaneous RAS positive malignancies	Permanently Discontinue
Uveitis	
Grade 1–3	If Grade 1 or 2 does not respond to specific ocular therapy, or for Grade 3 uveitis, withhold encorafenib and binimetinib for up to 6 weeks. 
• If improved, resume at same or reduced dose.• If not improved, permanently discontinue.
Grade 4	Permanently discontinue encorafenib and binimetinib.
Other Eye Disorders (i.e., non-Uveitis Events)	

Severity of Adverse Event	Dose Modification
Grade 1–2	Maintain dose level of encorafenib and binimetonib and increase frequency of ophthalmic monitoring to at least every 14 days until stabilization or resolution.
Grade 3	Interrupt dosing of encorafenib and binimetonib and refer patient to ophthalmologist within 7 days.
	
 1. If resolved to Grade \leq 1 in \leq 21 days, resume treatment at 1 reduced dose level of encorafenib and binimetonib. 2. If not resolved to Grade \leq 1 in \leq 21 days, permanently discontinue encorafenib and binimetonib and close follow-up with ophthalmic monitoring until stabilization or resolution.
Grade 4	Permanently discontinue encorafenib and binimetonib and immediate follow-up with ophthalmic monitoring until stabilization or resolution.
QTc Prolongation	
QTcF $>$ 500 ms and \leq 60 ms increase from baseline	
1st occurrence:
 
 • Temporarily interrupt dosing of encorafenib until QTcF $<$ 500 ms. Then resume treatment at 1 reduced dose level of encorafenib. 
2nd occurrence:
 
 • Temporarily interrupt dosing of encorafenib treatment until QTcF $<$ 500 ms. Then resume treatment at 1 reduced dose level of encorafenib. 
3rd occurrence:
 
 • Permanently discontinue encorafenib.
QTcF $>$ 500 ms and $>$ 60 ms increase from baseline	Permanently discontinue.

Severity of Adverse Event	Dose Modification
Dermatologic (Except Hand-foot Skin Reactions)	
Grade 2	If no improvement within 2 weeks, withhold until Grade 0–1. Resume at same dose if first occurrence or reduce dose if recurrent.
Grade 3	Withhold until Grade 0–1. Resume at same dose if first occurrence or reduce dose if recurrent
Grade 4	Permanently discontinue.
Hand-foot Skin Reaction (HFSR)/Palmar-plantar Erythrodysesthesia Syndrome (Dose Adjustment for Encorafenib ONLY)	
Grade 1	Maintain dose of encorafenib. Promptly institute supportive measures, such as topical therapy, for symptomatic relief. Give instruction on life-style modifications.

Severity of Adverse Event	Dose Modification
Grade 2	
1st occurrence:
 
• Maintain dose of encorafenib and HFSR should be closely monitored. Promptly institute supportive measures, such as topical therapy, for symptomatic relief. Give instruction on life-style modifications.• If no improvement \leq 14 days, interrupt dosing of encorafenib until resolved to Grade \leq 1. Resume treatment with encorafenib at current dose level. Continue supportive measures, such as topical therapy, for symptomatic relief. Give instruction on life-style modifications. 
Additional occurrence:
 
• Treatment with encorafenib may be maintained or interrupted based upon the Investigator's discretion. Continue supportive measures, such as topical therapy, for symptomatic relief. Give instruction on life-style modifications. 
If interrupted dosing of encorafenib per Investigator's judgment, interrupt until resolved to Grade \leq 1. Resume treatment with encorafenib at the same dose level or 1 reduced dose level based upon the Investigator's discretion.

Severity of Adverse Event	Dose Modification
Grade 3	
1st or additional occurrence:
 
 Interrupt dosing of encorafenib until resolved to Grade ≤ 1. Promptly initiate supportive measures, such as topical therapy, for symptomatic relief. Give instruction on life-style modifications. Reassess the patient weekly. Then resume treatment at one reduced dose level of encorafenib. Consider referral to dermatologist and manage HFSR per dermatologist's recommendation. 
3rd occurrence:
 
Interrupt dosing of encorafenib until resolved to Grade ≤ 1, decision to resume treatment with encorafenib at one reduced dose level or permanently discontinue encorafenib should be based upon the Investigator's discretion.

Nausea/Vomiting	
Grade 1–2 Grade 3	
Maintain dose level of encorafenib and binimatinib. Promptly institute antiemetic measure.
 
Interrupt dosing of encorafenib and binimatinib until resolved to Grade ≤ 1. Then resume treatment at 1 reduced dose level of encorafenib. Resume treatment with binimatinib at the current dose if, in the judgment of the Investigator, the toxicity is considered to be unrelated to binimatinib, or at 1 reduced dose level. Note: Interrupt dosing of encorafenib and binimatinib for \geq Grade 3 vomiting or Grade 3 nausea only if the vomiting or nausea cannot be controlled with optimal antiemetics (as per local practice).

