Concurrently, a triple therapy arm will be explored with encorafenib 300 mg PO QD together with ipilimumab administered IV at 1mg/kg and nivolumab 3mg/kg IV every 3 weeks for 4 doses, followed by nivolumab administered at 480mg every 4 weeks until progression or discontinuation due to toxicity.

Tolerability of the two arms will be compared, and a recommended phase II regimen (RP2R) will be determined.

After determination of treatment regimen, expansion cohorts will further explore the preliminary efficacy and further describe the toxicity profile of the triplet or quadruplet regimen in high-risk cohorts including symptomatic brain metastases or liver metastases with elevated lactate dehydrogenase (LDH) or bulky systemic disease burden.

Study Phase: 1/2

Research Hypothesis: Treatment with encorafenib + nivolumab + ipilimumab (triple therapy) and/or treatment with encorafenib + binimetinib + nivolumab + ipilimumab (quadruple therapy) will demonstrate adequate safety and tolerability in unresectable or metastatic *BRAF*-mutant melanoma high-risk patients.

Objectives

Primary Objective

- To nominate a recommended phase II regimen (RP2R) of triple or quadruple therapy with encorafenib (+/- binimetinib) + nivolumab and + ipilimumab in *BRAF*-mutated, metastatic melanoma.

Secondary Objectives

Phase I/II study of encorafenib with and without binimetinib with nivolumab and low dose ipilimumab in metastatic *BRAF* mutant melanoma

- To estimate the RECIST response rate of triple or quadruple therapy in high-risk populations of *BRAF*-mutated, metastatic melanoma.
- To estimate the CNS clinical benefit rate (CBR, defined as complete response [CR] + partial response [PR] + stable disease [SD] > 6 months) per RANO-MB criteria of triple or quadruple therapy in *BRAF*-mutated, metastatic melanoma to the CNS
- To describe the toxicity, using Criteria for Adverse Events version 5 (CTCAEv5), of triple or quadruple therapy in *BRAF*-mutated, metastatic melanoma
- To summarize the progression-free survival of triple or quadruple therapy in high-risk populations of *BRAF*-mutated, metastatic melanoma

Exploratory Objective

- To evaluate the association between treatment response and baseline tumor mutational burden, changes in the tumor microenvironment (interferon [*IFN*]-associated gene expression), T cell clonality, and other biospecimens before and after therapy.

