3. INVESTIGATIONAL PLAN

3.1 Study Design and Duration

This is an open label, multi-site, phase 1/2 study of encorafenib +/- binimatinib + nivolumab + ipilimumab for the treatment of participants with unresectable or metastatic *BRAF*-mutated melanoma in high risk cohorts.

Study participants will consist of metastatic melanoma patients harboring *BRAFV600E/K* mutation without previous frontline therapy or recently started treatment with up to 6 weeks of targeted therapy, or one cycle of immunotherapy (or >6 months from adjuvant therapy). Toxicity from prior treatment must have resolved to ≤ Grade 1 and not included previous Grade 3–4 irAEs that required treatment discontinuous or previous Grade 2 immune-related uveitis or pneumonitis.

Phase I, Cohort 1: Twelve patients will be treated with triple therapy: 300 mg encorafenib and 3mg/kg nivolumab and 1 mg/kg ipilimumab. Dose-limiting toxicity (DLT) for Cohort 1 will be evaluated at week 6.

[figure not shown]
Phase I, Cohort 2: Upfront quadruple therapy (450mg encorafenib, 45mg binimatinib, 3mg/kg nivolumab, and 1mg/kg ipilimumab) will be investigated with twelve patients. DLT for Phase I, Cohort 2 will be evaluated at week 6.

Prior studies with triplet therapies combining anti PD-1/PD-L1, *BRAF*, and MEK inhibition have shown Grade 3–4 AEs occurring from 58%–73%^{5,43,44,68}. These initial cohorts were small and did not use the newer, more potent and specific *BRAF*/MEK inhibitor pair encorafenib/binimatinib. We are allowing an initial DLT rate up to 75% in a continuous Bayesian monitoring protocol (See Statistics Section 8). We anticipate most of the toxicities to be additive and not synergistic and based on earlier recognition and treatment of immunotherapy AEs (see Appendix 6) and very specific AEs from encorafenib and binimatinib (see Appendix 2 and 3), we anticipate being able to create a safe RP2R dosing schedule.

Upon establishment of RP2R schedule, only participants with advanced melanoma who are either treatment naïve in the metastatic setting, have recently started treatment with targeted therapy within the past 6 weeks, or one cycle of immunotherapy, or who have progressed on adjuvant therapy more than 6 months following completion of adjuvant therapy (either *BRAF*-MEK or PD1 Ab) will be eligible for participation in high risk disease cohort expansion (Groups 1 or 2, see Schema below).

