cannot be below 0.35 mg/mL. It is not to be administered as an IV push or bolus injection. At the end of the infusion, flush the line with a sufficient quantity of normal saline.

Ipilimumab

Ipilimumab injection can be used for IV administration without dilution after transferring to a PVC (polyvinyl chloride), non-PVC/non-DEHP (di-(2-ethylhexyl)phthalate) or glass containers and is stable for 24 h at 2 °C–8°C or room temperature/room light (RT/RL). For ipilimumab storage instructions, refer to ipilimumab IB and/or pharmacy reference sheets. Recommended safety measures for preparation and handling include protective clothing, gloves, and safety cabinets.

Ipilimumab is to be administered as an IV infusion per institution SOC, using a volumetric pump with a 0.2 to 1.2 micron in-line filter at the protocol-specified dose. The drug can be diluted with 0.9% normal saline or 5% Dextrose Injection to concentrations between 1 mg/mL and 4 mg/mL. It is not to be administered as an IV push or bolus injection. Care must be taken to assure sterility of the prepared solutions, since the drug product does not contain any antimicrobial preservatives or bacteriostatic agents.

When both study drugs are to be administered on the same day, separate infusion bags and filters must be used for each infusion. Nivolumab is to be administered first. The nivolumab infusion must be promptly followed by a saline flush to clear the line of nivolumab before starting the ipilimumab infusion.

Encorafenib

Encorafenib 450 (quadruple) or 300 (triple) mg will be administered PO QD continuously. Patients should take encorafenib daily in the morning at approximately the same time every day.

Binimatinib

Binimatinib 45 mg will be administered PO BID continuously. Patients will be instructed to take binimatinib 12 ± 2 h apart in the morning and in the evening at approximately the same times every day.

Encorafenib and binimatinib should be taken together, if applicable, and without regard to food. Patients will be instructed to swallow the capsules/tablets whole with a large glass of water and not to chew or crush them.

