4.9 Management Guidelines for Targeted Therapy

See Appendix 2 and 3.

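### Appendix 2's encorafenib reduction table fits only the 450 mg quadruple start; for triple therapy its first reduction equals the 300 mg starting dose

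*Combined protocol and SAP*

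**What the plan says.** The protocol uses two encorafenib starting doses. Section 4.3 gives both: "Encorafenib 450 (quadruple) or 300 (triple) mg will be administered PO QD continuously". The Synopsis says "a triple therapy arm will be explored with encorafenib 300 mg PO QD", and Section 3.1 repeats the dose for Cohort 1: "Twelve patients will be treated with triple therapy: 300 mg encorafenib".

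For dose modification, Section 4.9 says only "See Appendix 2 and 3". Appendix 2 has a single table for encorafenib. The First Dose Reduction row is "300mg (four 75mg capsules) PO once daily", the second is 225 mg, the third is "150mg (two 75mg capsules) PO once daily", and any later modification is to discontinue. The table names no starting dose and has no column or footnote for the triple regimen.

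The event-specific rules in the same appendix work by relative steps. For the first or an additional Grade 3 hand-foot skin reaction, after interruption: "Then resume treatment at one reduced dose level of encorafenib". The QTc, Grade 3 other-eye-disorder and Grade 3 nausea/vomiting rules use the same kind of step. For a third Grade 3 hand-foot reaction, the investigator makes the "decision to resume treatment with encorafenib at one reduced dose level or permanently discontinue encorafenib".

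**The concern.** The row labels count reductions from 450 mg, and the event rules count them from the patient's current level. For a quadruple patient the two agree. For a triple patient they do not: the row labelled as the first reduction is the dose the patient is already taking, while the event rule asks for a lower one.

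A site that looks up the first reduction for a triple patient recovering from a Grade 3 toxicity would find 300 mg and could resume at full dose. The labels also show three reductions before discontinuation, when only two listed doses lie below 300 mg. In a multi-site study, the same toxicity could then be followed by different doses, or by stopping after a different number of steps.

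Appendix 3 does not have this problem. Binimetinib has one starting dose (45 mg twice daily), so its first-reduction label (30 mg twice daily) is correct wherever it applies.

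**Working it through.** The plan states no figure to reproduce. The check compares each row of the Appendix 2 table with each regimen's starting dose.

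Inputs: starting doses of 450 mg (quadruple) and 300 mg (triple) from Section 4.3; table rows of 300, 225 and 150 mg, then discontinue, from Appendix 2.

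Formula: row dose / starting dose.

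| Row label in Appendix 2 | Dose | Quadruple (450 mg) | Triple (300 mg) |
|---|---|---|---|
| First | 300 mg | 300/450 = 66.7% | 300/300 = 100% |
| Second | 225 mg | 225/450 = 50% | 225/300 = 75% |
| Third | 150 mg | 150/450 = 33.3% | 150/300 = 50% |
| Subsequent | stop | stop | stop |

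1. **Number of true reductions.** Quadruple has three (300, 225, 150 mg). Triple has two (225, 150 mg), because the first row leaves the dose unchanged.

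2. **First resumption dose for triple.** By the row label it is 300 mg, no reduction. By the event rules it is the next lower listed level, 225 mg, a reduction of (300 − 225)/300 = 25%.

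3. **Repeated Grade 3 hand-foot reaction, reading the rules as relative steps and assuming no other reductions.** Quadruple: 300 mg after the first, 225 mg after the second, then 150 mg or discontinuation at the third. Triple: 225 mg after the first, 150 mg after the second; at the third no lower level is listed, so of the two options offered only discontinuation remains. The last row of the table gives the same answer.

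4. **DLT criterion.** Section 4.7 counts inability to tolerate at least 66% of the planned encorafenib dose. At the disputed first step for triple, both candidate doses (100% and 75% of start) lie above 66%, so no effect on the DLT threshold is claimed.

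5. **Patients on the regimen.** Section 3.1 puts 12 patients in Cohort 1. Phase II adds up to 60, so the ceiling is 12 + 60 = 72 if triple is chosen and 12 if it is not. These count patients treated, not patients misdosed. The documents give no dose-reduction rate for this triplet. The reduction rates cited in Section 1.1.3.1 are for other regimens: 4/24 = 17% reducing one or both of encorafenib and binimetinib, and 28/125 = 22% on dabrafenib plus trametinib. If those rates were assumed, 12 × 4/24 = 2.0 to 12 × 28/125 = 2.7 of the 12 would need some reduction. Nothing in the documents says what share of them would be resumed at the wrong dose.

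**The case against.** The best defence is that the answer is already in the document. Moving from 300 mg to 300 mg is not a lower level, so a clinician told to resume one level down would go to 225 mg, then 150 mg, and would then reach the row that says to discontinue. On this view the first row is simply one that triple patients skip, and having fewer rungs from a lower start is arithmetic, not an error.

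Most of that stands. It settles what the intended ladder probably is, and it rules out two stronger readings that a reader might infer:

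- **That the number of reductions for triple is undefined.** The relative rules and the discontinuation row together give two.
- **That the third Grade 3 hand-foot reaction leaves a triple patient without an instruction.** The rule itself offers permanent discontinuation, and the table ends there. A quadruple patient already reduced for another toxicity can also be at 150 mg, so reaching the bottom of the ladder is not peculiar to triple.

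It is also true that many Appendix 2 rules do not force a reduction: first Grade 2 or 3 dermatologic events resume at the same dose, and uveitis may do so. The permanent-discontinuation rules in Section 4.10 apply whatever the ladder says.

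The defence does not make the row label correct. A table headed as dose reductions gives, for one of the two regimens, a first reduction equal to the starting dose. The reader has to override the label to follow the event rule.

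**Conclusion.** The table is wrong as written for triple therapy, and the error is minor. Its labels fit only the 450 mg start. For the 300 mg start, the first reduction is 100% of the starting dose and contradicts the instruction to step down a level. The implied ladder is 300 to 225 to 150 mg, then discontinue: two reductions against the three labelled. This rests on reading the event rules as steps from the patient's current dose, which is their natural meaning.

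The consequence is possible inconsistent dosing after toxicity among the 12 Cohort 1 patients, and in phase II only if triple is the recommended regimen. The number who would be misdosed cannot be estimated. A reader might infer that the toxicity data or the choice of regimen would be compromised; the documents do not support that. No effect on sample size, DLT thresholds, regimen selection or analysis is claimed.

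**What to change.** In Appendix 2, label the encorafenib ladder by starting dose:

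- **Quadruple:** 450 mg start; 300 mg (first), 225 mg (second), 150 mg (third); then discontinue.
- **Triple:** 300 mg start; 225 mg (first), 150 mg (second); then discontinue. Apply this ladder in phase II if triple is the recommended regimen.

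Add one sentence: at 150 mg, any further event for which Appendix 2 requires a dose reduction, for example a further Grade 3 hand-foot reaction, means discontinuing encorafenib. Limit it to such events. The Grade 1 and 2 hand-foot rules should stay as they are, because they maintain the dose or allow resumption at the same dose, and a blanket stop at 150 mg would contradict them.

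The cost is a few lines of text, with no change to visits, sample size or analysis. The downside is that triple has one fewer reduction step than quadruple. If the clinical team wants three, it has to add a level below 150 mg, which the documents do not give.

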APPENDIX 3 DOSE REDUCTION FOR BINIMETINIB RELATED ADVERSE EVENTS

Action	Recommended Dose
First Dose Reduction	30mg PO BID
Subsequent Modification	Discontinue

Severity of Adverse Event	Dose Modification
Cardiomyopathy	
Asymptomatic, absolute decrease in LVEF of > 10% from baseline that is also below the LLN	Withhold binimetinib for up to 4 weeks, evaluate LVEF every 2 weeks. Resume binimetinib at a reduced dose if the following are present: 
 • LVEF is at or above the LLN and • Absolute decrease from baseline is 10% or less and • Patient is asymptomatic. If LVEF does not recover within 4 weeks permanently discontinue binimetinib
Grade 3–4 (Symptomatic congestive heart failure or absolute decrease in LVEF of > 20% from baseline that is also below LLN)	Permanently discontinue binimetinib. Closely monitor LVEF until resolution or up to 16 weeks.
Venous Thromboembolism	
Uncomplicated DVT or PE	Withhold binimetinib. 
 • If improves to Grade 0–1, resume at a reduced dose. • If no improvement, permanently discontinue binimetinib. Permanently discontinue encorafenib and binimetinib.
Life Threatening PE	
Serous Retinopathy	

Severity of Adverse Event	Dose Modification
Symptomatic serous retinopathy/ Retinal pigment epithelial detachments	
Withhold binimetinib for up to 10 days.
 
 • If improves and becomes asymptomatic, resume at the same dose. • If not improved, resume at a lower dose level or permanently discontinue binimetinib
Retinal Vein Occlusion (RVO)	
Any Grade	Permanently discontinue binimetinib.
Uveitis	
Grade 1–3	
If Grade 1 or 2 does not respond to specific ocular therapy, or for Grade 3 uveitis, withhold binimetinib and encorafenib for up to 6 weeks.
 
 • If improved, resume at same or reduced dose. • If not improved, permanently discontinue binimetinib
Grade 4	Permanently Discontinue
Other Eye Disorders (i.e., Non-retinal Events, non-Uveitis Events)	

Severity of Adverse Event	Dose Modification
Grade 1–2	Maintain dose level of encorafenib and binimetinib and increase frequency of ophthalmic monitoring to at least every 14 days until stabilization or resolution.

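### In the quadruplet, Appendix 2's residual eye rows direct binimetinib without excluding retinal events, and so conflict with Appendix 3 on retinal vein occlusion and symptomatic serous retinopathy

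*Combined protocol and SAP*

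**What the plan says.** Appendix 2 covers encorafenib-related events. After its uveitis rows comes a block headed "Other Eye Disorders (i.e., non-Uveitis Events", and the appendix has no separate row for RVO or serous retinopathy. The block gives instructions for both targeted drugs at every grade:

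- Grade 1-2: "Maintain dose level of encorafenib and binimetonib and increase frequency of ophthalmic monitoring".
- Grade 3: interrupt both. If the event falls to Grade 1 or less within 21 days, "resume treatment at 1 reduced dose level of encorafenib and binimetonib"; otherwise stop both.
- Grade 4: "Permanently discontinue encorafenib and binimetonib and immediate follow-up with ophthalmic monitoring until stabilization or resolution".

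Appendix 3 covers binimetinib-related events. Its parallel block has a narrower heading, "Other Eye Disorders (i.e., Non-retinal Events, non-Uveitis Events", because retinal events have their own rows there. RVO of any grade ends binimetinib permanently. For symptomatic serous retinopathy or retinal pigment epithelial detachment, the instruction is "Withhold binimetinib for up to 10 days", then "If improves and becomes asymptomatic, resume at the same dose". Without improvement, the choice is a lower dose or a permanent stop.

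Section 4.9 refers the reader to both appendices and adds nothing else.

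**The concern.** A patient on the quadruplet takes both targeted drugs, so both appendices apply. An RVO or a serous retinopathy is an eye disorder that is not uveitis, so it fits the Appendix 2 heading as worded. It also fits a named row in Appendix 3, and the two tables can give different instructions for the same drug in the same patient.

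The difference matters most at Grade 1-2, where Appendix 2 is the less protective table: it continues a drug that Appendix 3 stops or holds. Low-grade retinal events on this drug pair appear in the protocol's own background. In the 24-patient encorafenib plus binimetinib series in Section 1.1.3.1, all adverse events were Grade 1-2 apart from one Grade 3 myalgia. Two patients had retinal detachment, and intra-retinal fluid in one patient cleared after binimetinib was held.

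**Working it through.** No arithmetic is involved. The check sets the two tables side by side for binimetinib and then looks for text that would settle a difference.

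**Step 1. Binimetinib instruction, as worded.**

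| Event and grade | Appendix 2, residual eye rows | Appendix 3, named rows | Result |
|---|---|---|---|
| RVO, Grade 1-2 | Continue, with closer eye monitoring | Permanent stop | Conflict; Appendix 2 less protective |
| RVO, Grade 3 | Interrupt; restart one level lower (45 to 30 mg BID) if Grade 1 or less within 21 days, otherwise stop | Permanent stop | Conflict if the event resolves |
| RVO, Grade 4 | Permanent stop | Permanent stop | Agree |
| Symptomatic serous retinopathy, Grade 1-2 | Continue, with closer eye monitoring | Hold for up to 10 days | Conflict; Appendix 2 less protective |
| Symptomatic serous retinopathy, Grade 3 | Interrupt; lower dose if resolved within 21 days, otherwise stop | Hold for up to 10 days; same dose if improved and symptom-free, otherwise lower dose or stop | Restart dose differs, with Appendix 2 stricter; if unresolved, stopping satisfies both |
| Symptomatic serous retinopathy, Grade 4 | Permanent stop | Hold, with possible restart (row is not graded) | Differ; Appendix 2 stricter |

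The point rests on the two Grade 1-2 rows and on resolved Grade 3 RVO.

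**Step 2. Is there a rule that decides between them?**

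- Section 4.9 names both appendices and sets no order.
- The attribution rule in Section 4.7 separates targeted therapy from immunotherapy. It does not separate encorafenib from binimetinib.
- Table 4.2 in Section 4.8 marks visual changes for both targeted drugs.
- Section 4.7 makes ophthalmically confirmed RVO a DLT without a grade threshold. That fixes DLT status and does not set the binimetinib dose.
- Section 4.10, even if read as covering the targeted drugs, does not reach Grade 1-2 RVO or serous retinopathy as such. At Grade 2 it catches only eye pain or blurred vision that fails topical treatment without improving to Grade 1, or that needs systemic treatment. It would end treatment for a Grade 3 event lasting more than 7 days, which leaves the Grade 3 RVO conflict for shorter events.

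**Step 3. Were the Appendix 2 eye rows meant for encorafenib alone?** The appendix does not read that way. Its hand-foot block is expressly limited to encorafenib, and its Grade 3 nausea and vomiting row lets the investigator judge whether binimetinib is implicated. The eye rows have neither limit and name binimetinib at every grade.

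**Step 4. Can a frequency be attached?** No. The documents give no RVO rate, and exclusion criterion 14 removes patients with RVO history or current RVO risk factors. How RVO would be graded depends on CTCAE v5, which the protocol only links to. The 20% for serous retinopathy in Section 1.1.2.2 covers all grades, with no symptomatic share. The series in Section 1.1.3.1 does not give symptom status.

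**The case against.** The best answer is that the appendices are organised by drug. RVO and serous retinopathy are named only in the binimetinib appendix, with binimetinib-only actions, and the Appendix 2 block is residual. Someone holding both tables would ordinarily apply the specific row. The any-grade DLT rule for RVO makes it less likely still that an investigator would treat RVO as a routine eye event, and in the cited series the intra-retinal fluid was managed by holding binimetinib, as Appendix 3 would have it for a symptomatic event.

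Most of this stands, and it limits the practical risk. It does not remove the conflict, because the Appendix 2 rows dose binimetinib themselves and the priority of Appendix 3 has to be inferred.

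A reader might also infer more than the documents support:

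- That binimetinib will in practice be continued through RVO. The natural reading points the other way.
- That the 20% rate or the case series can be turned into an expected number of affected patients. Neither identifies symptomatic events.
- That every difference in the table is a hazard. At Grade 3-4 serous retinopathy Appendix 2 is the stricter table, and for an unresolved Grade 3 event one action complies with both.

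**Conclusion.** The point holds as a minor conflict in a safety instruction. For binimetinib, the Appendix 2 wording says continue at Grade 1-2 RVO and Grade 1-2 symptomatic serous retinopathy, and allows a reduced-dose restart after resolved Grade 3 RVO. Appendix 3 says stop, hold and stop respectively, and no text states which prevails.

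The scope is Cohort 2 (12 patients) and Phase II (up to 60) only if the quadruplet becomes the recommended regimen. Those are the patients to whom the instruction would apply, not a forecast of events. The triplet contains no binimetinib and is unaffected. Nothing here bears on sample size, error rates or the DLT count. The conclusion assumes only that the Appendix 2 heading means what it says. It is firm on the wording and makes no claim about how often the wording would change care.

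**What to change.** Add one line to the Appendix 2 eye block:

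> For RVO and symptomatic serous retinopathy/retinal pigment epithelial detachment, binimetinib follows the named rows in Appendix 3; for these events the grade-based rows below apply to encorafenib only.

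Copying the narrower Appendix 3 heading into Appendix 2 would not be enough, because encorafenib would then have no rule for retinal events.

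The sponsor should confirm two things when adopting the line. First, the encorafenib action once binimetinib is stopped permanently: continuing unchanged leaves 450 mg encorafenib without binimetinib, whereas the binimetinib-free arm (Section 3.1, Cohort 1) uses 300 mg, which is also the first reduction level in Appendix 2. Second, that the ungraded Appendix 3 row is intended for Grade 3-4 serous retinopathy, where it is the less strict of the two.

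The cost is one line by amendment, with no change to design, sample size or data collection.
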